## **11.10 LIMITATIONS OF THE RESEARCH METHODS**

The main foreseen limitations for this study are attributed to its observational design and mainly involve patient selection bias, information bias and missing data as well as lack of internal validity (no control group).

In order to control for and minimize patient selection bias, physicians will be requested to consecutively, thus non-selectively, enroll the first patients (based on the site-specific target) attending their clinic that meet the study specific eligibility criteria. In addition the investigators' decision-making to administer afatinib to a patient will be based on current medical practice and precede the consideration of the patient's eligibility for enrolment into the study. A screening log of all potentially eligible patients will be kept at site.

With regard to patient information/recall bias that may be introduced by the collection of data pertaining to patient-reported outcomes, this will be mitigated through the use of widely used PROs that employ no recall period as all questions refer to the symptoms and state of health at the day of completion. In addition, the self-administered PROs shall be completed by the patients themselves before the performance of any study-specific procedure(s) or clinical assessment(s) in order to avoid introducing any response bias.

In regards to the patient-reported symptom and HRQoL outcome measures, a potential confounding factor may arise from the fact that for patients for whom the onset of treatment with afatinib precedes their enrolment in the study, the completion of the PROs will not accurately reflect their baseline symptom burden and health state; nevertheless since the permitted time window between these two time points has been set at a maximum of 7 days, this time lag is not expected to significantly impact the robustness of the outcomes.

Another confounding factor to the patient-reported symptom and HRQoL outcomes is the potential effects of comorbidities and concomitant medications. To account for this, all baseline comorbid conditions as well as of concomitant medications both at baseline and throughout the conduct of the study (*with particular emphasis among others on analgesics, antitussives, antidepressants, antiemetics, and antidiarrheals*) will be collected in order to differentiate anticancer treatment effect from the effects of comorbidities and concomitant medication.

The possible influence of confounding factors on the outcomes of this study will be accounted for in the statistical analyses by use of robust multivariable analyses, if deemed necessary.

With regard to the external validity i.e., the ability to generalize the study results to a more universal population, every effort will be made for the study population to be representative of the overall population of patients with NSCLC treated with afatinib in Greece by enrolling patients from geographically diverse locations throughout Greece with a non-limiting set of clinical characteristics, apart from those indicated by the locally approved product's SmPC, accounting for variations in medical practice paradigms.

Internal validity of the outcomes will be safeguarded to the extent feasible with the implementation of appropriate source data verification and quality assurance measures, as described in the relevant Section [11.9](#).

## **11.11 OTHER ASPECTS**

### **11.11.1 Informed consent, data protection, study records**

The study will be carried out in compliance with the protocol, the principles laid down in the Declaration of Helsinki, in accordance with the ICH Harmonised Tripartite Guideline for GCP and relevant BI Standard Operating Procedures (SOPs). Standard medical care (prophylactic, diagnostic and therapeutic procedures) remains in the responsibility of the treating physician of the patient.

The investigator should inform the sponsor immediately of any urgent safety measures taken to protect the study subjects against any immediate hazard, and also of any serious breaches of the protocol/ICH GCP.

The rights of the investigator and of the sponsor with regard to publication of the results of this study are described in the investigator contract. As a general rule, no study results should be published prior to finalisation of the CSR.

#### 11.11.1.1 Study approval, patient information, and informed consent

This study will be initiated only after all required legal documentation has been reviewed and approved by the respective Institutional Review Board (IRB)/Independent Ethics Committee (IEC) and competent authority (CA), where applicable, according to national and international regulations. The same applies for the implementation of changes introduced by amendments.

In particular, as per the national regulatory requirements, the protocol and the informed consent form (ICF) must be submitted to the IRBs (Scientific Council/Board of Directors) of the participating hospitals as part of the approval process. The Scientific Council/Board of Directors of the participating hospitals must also approve any amendment to the protocol or Patient ICF, prior to the implementation of the amendment or the use of the ICF, according to local regulations. The conduct of this non interventional study will adhere to the applicable national regulatory requirements governing the conduct of such type of clinical studies.

Prior to patient participation in the study, written informed consent must be obtained from each patient (or the patient's legally accepted representative) according to ICH GCP and to the national regulatory and legal requirements. Each signature must be personally dated by each signatory and the informed consent and any additional patient-information form retained by the investigator as part of the study records. A signed copy of the informed consent and any additional patient information must be given to each patient or the patient's legally accepted representative.

The patient must be informed that his/her personal study-related data will be used by Boehringer Ingelheim in accordance with the local data protection law. The level of disclosure must also be explained to the patient.

The patient must be informed that his/her medical records may be examined by authorised monitors (CML/CRA) or Clinical Quality Assurance auditors appointed by Boehringer Ingelheim, by appropriate IRB/IEC members, and by inspectors from regulatory authorities.

#### 11.11.1.2 Data quality assurance

A quality assurance audit/inspection of this study may be conducted by the sponsor or sponsor's designees or by IRBs/IECs or by regulatory authorities. The quality assurance auditor will have access to all medical records, the investigator's study-related files and correspondence, and the informed consent documentation of this study.

#### 11.11.1.3 Records

Case Report Forms (CRFs) for individual patients will be provided by the sponsor via an Electronic Data Capture (EDC) system.

##### 11.11.1.3.1 Source documents

Source documents provide evidence for the existence of the patient and substantiate the integrity of the data collected. Source documents are filed at the investigator's site.

Data entered in the eCRFs that are transcribed from source documents must be consistent with the source documents or the discrepancies must be explained. The investigator may need to request previous medical records or transfer records; also current medical records must be available.

All data entered in the eCRFs must be derived from source documents.

#### **11.11.1.3.2 Direct access to source data and documents**

The investigator/institution will permit study-related monitoring, audits, IRB/IEC review and regulatory inspection, providing direct access to all related source data / documents. eCRFs and all source documents, including progress notes and copies of laboratory and medical test results must be available at all times for review by the sponsor's clinical study monitor, auditor and inspection by health authorities (e.g. FDA). The Clinical Research Associate (CRA)/on site monitor and auditor may review all eCRFs, and written informed consents. The accuracy of the data will be verified by reviewing the documents described in Section [11.11.1.3.1](#).

#### **11.11.1.3.3 Storage and retention of records**

Patient files and other source documents must be kept for the maximum period of time permitted by the hospital/institution, or as specified below. The Clinical Research Associate (CRA)/on site monitor must be consulted if the investigator wishes to assign the files to someone else, remove them to another location, or if he/she is unable to retain them for the specified period.

The investigator must retain study records (*e.g., source documents such as medical records, contracts, e-archivals and signed consent forms*) for the amount of time specified by applicable laws and regulations. At a minimum, study records must be retained for the amount of time specified by the standing legislation, i.e., study records must be retained for at least 5 years after study completion. These documents should be retained for a longer period however if required by the applicable regulatory requirements or by an agreement with the study sponsor.

#### **11.11.1.4 Statement of confidentiality**

Individual patient medical information obtained as a result of this study is considered confidential and disclosure to third parties is prohibited with the exceptions noted below. Patient confidentiality will be ensured by using patient identification code numbers.

Treatment data may be given to the patient's personal physician or to other appropriate medical personnel responsible for the patient's welfare. Data generated as a result of the study need to be available for inspection on request by the participating physicians, the sponsor's representatives, by the IRB/IEC and the regulatory authorities, i.e. the CA.

#### **11.11.1.5 Completion of study**

The IRB (Scientific Council/Board of Directors) of the participating hospital sites will be notified about the end of the study (last patient out) or early termination of the study,

Proprietary confidential information © 2018 Boehringer Ingelheim International GmbH or one or more of its affiliated companies

unless otherwise mandated by the national regulations governing the conduct of such type of studies which may have been altered by the time of study completion.

## **12. PROTECTION OF HUMAN SUBJECTS**

By signing this protocol, the investigator agrees to treat all patient data used and disclosed in connection with this study in accordance with all applicable privacy laws, rules and regulations.

The confidentiality of patient data will be maintained at all times and no documents containing the patient's name or other identifying information will be collected by the Sponsor. It may be necessary for the sponsor's representatives, the IRBs and regulatory authority representatives to have direct access to the patient's medical records. If study documents need to be photocopied during the process of verifying eCRF data, the patient will be identified by a unique code only; full names/initials and other identifying information will be masked.

By signing this protocol, the investigator also affirms to the sponsor that information provided to the investigator by the sponsor will be maintained in confidence and will be divulged only as necessary to the IRBs and institution employees directly involved in the study. IRB members and employees also understand the confidentiality requirements for any information divulged to them. The data generated by this study will be considered confidential by the investigator, except to the extent that it is included in a publication as agreed in the publication policy of this protocol.

By signing the ICF, the patient accepts being informed of the following:

- What kind of personal information (data) will be collected from participants in this study;
- Who will have access to that information and why;
- Who will use or disclose that information;
- What are the rights of a research participants pertaining to the potential revoke of their authorization for use of their personal data.

In case of patient authorization revoking, the investigator maintains the right to use the information collected prior to the revoke.

## **13. MANAGEMENT AND REPORTING OF ADVERSE EVENTS/ADVERSE REACTIONS**

### **13.1 DEFINITIONS OF ADVERSE EVENTS**

#### Adverse event

An adverse event (AE) is defined as any untoward medical occurrence in a patient or clinical investigation subject administered a medicinal product and which does not necessarily have a causal relationship with this treatment. An adverse event can therefore be any unfavourable and unintended sign (e.g. an abnormal laboratory finding), symptom, or disease temporally associated with the use of a medicinal product, whether or not considered related to the medicinal product.

#### Adverse reaction (ADR)

An adverse reaction is defined as a response to a medicinal product which is noxious and unintended. Response in this context means that a causal relationship between a medicinal product and an adverse event is at least a reasonable possibility. Adverse reactions may arise from use of the product within or outside the terms of the marketing authorisation or from occupational exposure. Conditions of use outside the marketing authorisation include off-label use, overdose, misuse, abuse and medication errors.

#### Serious adverse event

A serious adverse event is defined as any AE which

- results in death,
- is life-threatening,
- requires in-patient hospitalisation, or
- prolongation of existing hospitalisation,
- results in persistent or significant disability or incapacity, or
- is a congenital anomaly/birth defect.

Life-threatening in this context refers to a reaction in which the patient was at risk of death at the time of the reaction; it does not refer to a reaction that hypothetically might have caused death if more severe.

Medical and scientific judgment should be exercised in deciding whether other situations should be considered serious reactions, such as important medical events that might not be immediately life threatening or result in death or hospitalisation but might jeopardise the patient or might require intervention to prevent one of the other outcomes listed above. Examples of such events are intensive treatment in an emergency room or at home for allergic bronchospasm, blood dyscrasias or convulsions that do not result in hospitalisation or development of dependency or abuse. Any suspected transmission via a medicinal product of an infectious agent is also considered a serious adverse reaction.

Every new occurrence of cancer is to be considered as SAE regardless of the duration between discontinuation of the study medication and the occurrence of the cancer.

**Protocol-specified adverse events of special interest (AESIs)**

There are no Protocol-specified Adverse Events of Special Interest for this study.

**13.2 ADVERSE EVENT AND SERIOUS ADVERSE EVENT  
COLLECTION AND REPORTING**

The investigator shall maintain and keep detailed records of all AEs in their patient files.

**Collection of AEs**

The study design is of non-interventional nature and the study is conducted within the conditions of the approved marketing authorisation. Sufficient data from controlled interventional trials are available to support the evidence on the safety and efficacy of the studied BI drug. For this reason the following AE collection and reporting requirements have been defined.

The following must be collected by the investigator in the eCRF from signing the informed consent onwards until the end of the study:

- all ADRs (serious and non-serious),
- all AEs with fatal outcome,
- all AEs which are relevant for a serious ADR or an AE with fatal outcome.

All ADRs, including those persisting after study completion must be followed up until they are resolved, have been sufficiently characterized, or no further information can be obtained.

The investigator carefully assesses whether an AE constitutes an ADR using the information below.

**Causal relationship of adverse event**

The definition of an adverse reaction implies at least a reasonable possibility of a causal relationship between a suspected medicinal product and an adverse event. An adverse reaction, in contrast to an adverse event, is characterised by the fact that a causal relationship between a medicinal product and an occurrence is suspected.

Medical judgment should be used to determine the relationship, considering all relevant factors, including pattern of reaction, temporal relationship, de-challenge or re-challenge, confounding factors such as concomitant medication, concomitant diseases and relevant history.

Arguments that may suggest a **reasonable causal relationship** could be:

- The event is **consistent with the known pharmacology** of the drug
- The event is known to be caused by or **attributed to the drug class**.
- A **plausible time to onset of the event** relative to the time of drug exposure.
- Evidence that the **event is reproducible** when the drug is re-introduced.

- **No medically sound alternative etiologies** that could explain the event (e.g. preexisting or concomitant diseases, or co-medications).
- The event is typically **drug-related and infrequent in the general population** not exposed to drugs (e.g. Stevens-Johnson syndrome).

Arguments that may suggest that there is **no reasonable possibility of a causal relationship** could be:

- No plausible time to onset of the event relative to the time of drug exposure is evident (e.g. pre-treatment cases, diagnosis of cancer or chronic disease within days/weeks of drug administration; an allergic reaction weeks after discontinuation of the drug concerned)
- Continuation of the event despite the withdrawal of the medication, taking into account the pharmacological properties of the compound (e.g. after 5 half-lives).
- Of note, this criterion may not be applicable to events whose time course is prolonged despite removing the original trigger.
- Additional arguments amongst those stated before, like alternative explanation (e.g. situations where other drugs or underlying diseases appear to provide a more likely explanation for the observed event than the drug concerned).
- Disappearance of the event even though the study drug treatment continues or remains unchanged.

#### Intensity of adverse event

The intensity of adverse events should be classified and recorded according to the NCI CTCAE version 4.0 [June 2010], in the eCRF.

The NCI CTCAE V4.0 can be viewed on-line at the following NCI weblink:

[ctep.cancer.gov/protocolDevelopment/electronic\\_applications/ctc.htm#ctc\\_40](http://ctep.cancer.gov/protocolDevelopment/electronic_applications/ctc.htm#ctc_40).

If a specific event is not included in the NCI CTCAE toxicity scale, the following scale should be used to grade that specific event:

**Table 3: Grading Scale for Toxicities Not Included in the NCI CTCAE**

Grade	Definition
1	Mild; Awareness of sign(s) or symptom(s) which is/are easily tolerated
2	Moderate; Enough discomfort to cause interference with usual activity
3	Severe; Incapacitating or causing inability to work or to perform usual activities

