#### **11.8.4 Analyses for the safety data**

All recorded AEs will be mapped by system organ class (SOC) and preferred term (PT) according to MedDRA (*most updated version at the point of coding*).

The number and proportion of patients experiencing any serious or non-serious adverse event will be calculated by SOC and PT.

Specifically, the following data will be tabulated:

- Number and proportion of patients experiencing a serious AE (SAE) by SOC and PT.
- Number and proportion of patients experiencing a non-serious AE (NSAE) by SOC and PT.
- Distribution of AEs by National Cancer Institute (NCI) Common Toxicity Criteria for Adverse Events (CTCAE) toxicity grade classification and causal relationship to study treatment.

Additionally, the exposure adjusted incidence rates (EAIRs) along with the respective 95% CIs will be calculated for the following patient subpopulations: those experiencing at least one SAE, at least one NSAE.

Available data from other safety-related evaluations (systolic and diastolic arterial blood pressure, respiratory rate and pulse rate) will be summarized descriptively per visit or when they occurred, along with the respective change from baseline to all post-baseline visits.

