## Statistical Analysis Plan

- ✓ Ongoing (yes, no);
- ✓ Causally related with GIOTRIF® (yes, no);
- ✓ Intensity according to National Cancer Institute (NCI) Common Terminology Criteria for Adverse Events (CTCAE) (Grade 1 or mild, Grade 2 or moderate, Grade 3 or high, Grade 4 or life-threatening, Grade 5 or death);
- ✓ Actions taken regarding GIOTRIF® for management of AE (none, dose reduction, permanent discontinuation, dose increase, completion of treatment according to protocol, treatment interruption and re-initiation, not applicable);
- ✓ Outcome (recovery, has not yet been recovered/ongoing, recovery with sequelae, death, unknown);
- ✓ Seriousness (yes, no).

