### **9.2 Adverse events**

The following adverse events are collected from the time the patient has signed the informed consent until the completion of his/her participation in the study: all serious and non-serious adverse drug reactions (ADRs) related to GIOTRIF; all AEs with fatal outcome (regardless of causal relationship with GIOTRIF); and all AEs (serious and non-serious) which are relevant to a serious ADR or to an AE with fatal outcome. An ADR is defined as a response to a medicinal product which is noxious and unintended. Response in this context means that a causal relationship between a medicinal product and an adverse event is at least a reasonable possibility.

All recorded adverse events will be mapped by LLT, PT and SOC according to MedDRA (the most updated version available at the time of coding onset). If two or more AEs (PTs) are reported as a unit, the individual terms will be reported as separate events.

A descriptive summary table will be created with the number and proportion of patients experiencing at least one adverse drug reaction regardless of seriousness (N)SADR, serious adverse drug reaction (SADR), non-serious adverse drug reaction (NSADR) and SAE. The percentage of patients who discontinued their treatment with afatinib due to AEs will also be tabulated.

Additionally, the following data will be provided in frequency tables:

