## Statistical Analysis Plan

- ✓ Number and percentage of patients experiencing at least one (N)SADR by SOC and PT.
- ✓ Number and percentage of patients experiencing at least one SADR by SOC and PT.
- ✓ Number and percentage of patients experiencing at least one NSADR by SOC and PT.
- ✓ Number and percentage of patients experiencing at least one SAE by SOC and PT.

*The aforementioned analysis will also be performed by outcome and action taken with afatinib.*

- ✓ Number and percentage of patients experiencing at least one (N)SADR by SOC, PT and NCI CTCAE grade.
- ✓ Number and percentage of patients experiencing at least one SADR by SOC, PT and NCI CTCAE grade .
- ✓ Number and percentage of patients experiencing at least one NSADR by SOC, PT and NCI CTCAE grade .
- ✓ Number and percentage of patients experiencing at least one SAE by SOC, PT and NCI CTCAE grade .

A patient data listing of all reported AEs will also be created and presented. The listing will include information related to the reported events [i.e. patient ID, center ID, verbatim term of AE, MedDRA terms (LLT, PT, SOC), onset date of AE, end date, outcome, causal relationship with afatinib, NCI CTCAE grade, seriousness, action(s) taken].

Additionally, the exposure-adjusted incidence rates (EAIRs) along with the respective 95% CI will be calculated for those experiencing at least one (N)SADR, at least one SADR, at least one NSADR.

Specifically, the EAIR is defined as the number of patients with a specific event divided by the total exposure-time in subject-year:

$$EAIR = \frac{n}{\sum t_i} \times 100$$

where n is the number of patients with at least one event and  $t_i$  is a patient's follow-up in subject-years.

If a patient has multiple events, then  $t_i$  is defined as the time from treatment onset to the occurrence of the first event. For a patient without any event, the  $t_i$  will be censored at the last follow-up time for that patient. The respective 95% CIs will also be calculated as follows:

$$\text{Lower confidence limit: } LCL = \frac{0.5c_{\alpha/2,2D}}{T} \text{ for } D > 0, 0 \text{ otherwise}$$

$$\text{Upper confidence limit: } UCL = \frac{0.5c_{1-\alpha/2,2D+2}}{T},$$

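### Protocol Table 3 gives events outside the CTCAE no grade above 3, the SAP intensity variable runs to Grade 5, and neither document says how the two scales meet in the by-grade safety tables

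*Protocol*

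**What the plan says.** Protocol section 13.2, under Intensity of adverse event, requires grading by CTCAE version 4.0 and gives a fallback: "If a specific event is not included in the NCI CTCAE toxicity scale, the following scale should be used to grade that specific event". That scale is Table 3. It has Grade 1 (mild), Grade 2 (moderate) and Grade 3, defined as "Severe; Incapacitating or causing inability to work or to perform usual activities". It has no row for a life-threatening or a fatal event.

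SAP section 2.2.2 lists a single CTCAE intensity variable for adverse events with five categories, ending in "Grade 3 or high, Grade 4 or life-threatening, Grade 5 or death". It gives no separate list for events that the CTCAE does not contain.

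Fatal events are collected by design. Protocol section 13.2, under Collection of AEs, names "all AEs with fatal outcome" as one of three classes to be recorded, and SAP section 9.2 adds that this applies whether or not the event is related to afatinib.

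Grade is then reported. Protocol section 11.8.4 plans a distribution of events by CTCAE "toxicity grade classification and causal relationship to study treatment". SAP section 9.2 has four by-grade tables, one each for all drug reactions, serious reactions, non-serious reactions and serious adverse events; the last is specified as "Number and percentage of patients experiencing at least one SAE by SOC, PT and NCI CTCAE grade".

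**The concern.** The study does not collect every adverse event. It collects drug reactions, fatal events, and events relevant to a serious reaction or a fatal event. Severe and fatal events are therefore a deliberate focus of the safety data, yet the fallback scale cannot express the two highest severities.

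Three things could follow:

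- The by-grade tables could show too few Grade 4 and Grade 5 events.
- The patient listing, which prints outcome and grade together, could pair an outcome of death with Grade 3.
- The same event could be graded differently at different sites among the seven planned, depending on whether the site applied Table 3 or the five categories of the SAP variable.

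For life-threatening events that the patient survives, grade carries particular weight. The outcome field in SAP section 2.2.2 has no life-threatening category and seriousness is recorded only as yes or no. Apart from the verbatim description, grade is the only listed variable that separates such an event from other serious events.

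**Working it through.** The plan gives no figure to reproduce here. The check sets the two scales side by side and follows an event through them.

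| Severity | Protocol Table 3 | SAP section 2.2.2 |
|---|---|---|
| Mild | 1 | 1 |
| Moderate | 2 | 2 |
| Severe / high | 3 | 3 |
| Life-threatening | none | 4 |
| Death | none | 5 |

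1. **Which scale applies.** For an event outside the CTCAE, Protocol section 13.2 points to Table 3. The SAP variable makes no exception for such events and offers all five categories.

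2. **Literal use of Table 3.** A life-threatening event can receive at most Grade 3, which is 4 - 3 = 1 grade below its SAP category. A fatal event can also receive at most Grade 3, which is 5 - 3 = 2 grades below.

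3. **Use of the SAP list.** The same events would be recorded as Grade 4 and Grade 5.

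4. **What reaches the tables.** SAP section 9.2 tabulates by CTCAE grade. It has no rule for events graded on Table 3, and section 2.2.2 lists no field that records which scale was used. The tabulated grade is therefore undetermined between 3 and 4, or between 3 and 5.

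5. **Which tables are open to this.** A fatal event is serious under Protocol section 13.1, so it falls in the by-grade table of serious adverse events even if unrelated to afatinib. A life-threatening or fatal reaction falls in the by-grade tables of all reactions and of serious reactions as well.

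6. **What is not affected.** Outcome, including death, and seriousness are separate fields in SAP section 2.2.2. SAP section 9.2 repeats the reaction and serious-event tables by outcome and by action taken, and the listing shows outcome, grade and seriousness for each event. The exposure-adjusted incidence rates use patient counts and follow-up time, not grade.

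7. **How many events.** The documents give no rate of events outside the CTCAE and do not reproduce the CTCAE, so no count or range can be derived.

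**The case against.** The strongest case against is that little can go wrong. Nothing in the SAP caps an event outside the CTCAE at Grade 3; its list carries plain labels for life-threatening and death that a site could apply to any event. No death is lost, because outcome and seriousness are recorded separately, deaths are tabulated by outcome, and an outcome of death beside Grade 3 would be visible in the listing. Fatal events and serious reactions must also be reported within 24 hours under Protocol section 13.2. A mild, moderate, severe scale used beside separate seriousness and outcome fields is a coherent choice. The affected set needs an event that is absent from the CTCAE, life-threatening or fatal, and graded literally by Table 3, and it may be empty. The eCRF itself is not in the documents, so divergent grading between sites is possible but not shown.

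Most of this stands and limits the point. A reader might infer that every such event will be tabulated as Grade 3 at most, or that each one is misplaced by one or two grades. The documents do not support that: they leave the grade open because the two scales conflict, and the displacement occurs only where Table 3 was followed. A reader might also infer that fatal events disappear from the safety report; the outcome tables and the listing show otherwise.

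What the objection does not remove is the conflict. The protocol instructs sites to use a scale that lacks two of the SAP's categories, and no rule joins them. For life-threatening events that are not fatal, the outcome field gives no backup.

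**Conclusion.** The point holds in a limited form. Table 3 and the SAP intensity variable are inconsistent for events outside the CTCAE, and the by-grade tables would show a life-threatening or fatal event of this kind as Grade 3 if Table 3 was followed. Sites using the five categories could grade the same event differently. The effect is confined to the by-grade safety tables and the grade column of the listing; deaths stay visible elsewhere. The number of events is unknown and probably small. The primary endpoint, sample size and analysis sets are untouched, and the study is descriptive, so this is a minor matter worth correcting because the correction is cheap.

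Two assumptions carry the conclusion. The first is that Table 3 is complete with three rows, as it reads. The second is that no site instruction outside the two documents, such as the Investigator Instructions Manual named in Protocol section 11.7, already settles how these events are graded.

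**What to change.** - **SAP section 9.2:** state that events graded on Table 3 are tabulated on the 1-5 scale of section 2.2.2, with life-threatening events as Grade 4 and deaths as Grade 5.
- **Before database lock:** check that every adverse event with outcome death is Grade 5, and query mismatches. Include events already graded under Table 3, since data collection began on 01 March 2016 (Protocol section 8). As the outcome field does not identify survived life-threatening events, serious events outside the CTCAE recorded as Grade 3 should be queried too.
- **Protocol Table 3:** add matching Grade 4 and Grade 5 rows at the next amendment. An amendment for this alone is not needed if the SAP rule is in place.

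The change is not free. It brings a small amount of query and re-grading work; adding rows without re-grading earlier events would leave mixed grading in the database. Changing the protocol table also needs approval from the Scientific Council/Board of Directors of each participating hospital (Protocol section 11.11.1.1). The SAP rule and the check avoid that step.
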